6.14.3 Vital Signs

Controlled Quality Management Document		
	Sponsor: Veru Inc.	
	Protocol Number: V3011902	
STATISTICAL ANALYSIS PLAN. PHASE 2-3-4		

Descriptive statistics for observed values and changes from baseline in the following vital signs will be presented by treatment group and visit:

- Systolic blood pressure (mmHg)
- Diastolic blood pressure (mmHg)
- Pulse rate (bpm)
- Respiration rate (breath / min)
- Body weight (kg)
- Body temperature (degrees Celsius)
- SpO₂ (%)

When study day has more than one record (i.e. vital sign log data) then summary table will use the average within the day.

Data for body temperature and SpO₂ log will be presented in plot where individual subjects will be overlaid in one figure (spaghetti plot) by treatment group.

All vital sign data will be listed.

6.14.4 Physical Examination

Shift tables for each body system from baseline to worst post-baseline record will be presented (Normal, Abnormal NCS and Abnormal CS). NCS = Not Clinically Significant, CS = Clinically Significant.

All physical examination data will be listed.

6.14.5 ECG Data

Descriptive statistics for observed values and changes from baseline in the following ECG variables will be tabulated at each follow-up visit:

- Heart rate (bpm)
- PR interval (ms)
- RR interval (ms)
- QRS duration (ms)
- QT interval (ms)

Controlled Quality Management Document		
	Sponsor:	Veru Inc.
	Protocol Number:	V3011902
STATISTICAL ANALYSIS PLAN. PHASE 2-3-4		

- QTc interval (ms)
- QTc interval (ms) [Bazett's formula - QTcB]
- QTc interval (ms) [Fridericia's formula - QTcF]

Shift tables in relation to the overall interpretation (Normal, Abnormal NCS and Abnormal CS) from baseline to worst post-baseline record will be presented.

All ECG data will be listed.

6.14.6 Chest X-Ray

Shift tables for chest X-ray from baseline to each timepoint will be presented (Normal, Abnormal).

All chest X-ray data will be listed.

7 INTERIM ANALYSIS

Interim analyses are described in separate IDMC SAP.

8 INDEPENDENT DATA MONITORING COMMITTEE (IDMC) ANALYSIS

Independent Data Monitoring Committee (IDMC) analyses and interim analyses are described in separate IDMC analysis plan.

9 CHANGES TO PLANNED PROTOCOL ANALYSIS

Original protocol stated that randomization will be stratified by WHO scores 5 and 6 but it was updated to include WHO scores 4, 5 and 6 in protocol version 3.0 (amendment 2)(dated 12-MAY-2021).

In the protocol WHO score was planned to be analyzed as continuous variable using MMRM. However this was changed into responder type of analysis in the SAP.

Holm step-down procedure was added to control multiplicity for primary endpoint and key secondary endpoints.

Controlled Quality Management Document		
	Sponsor:	Veru Inc.
	Protocol Number:	V3011902
STATISTICAL ANALYSIS PLAN. PHASE 2-3-4		

[REDACTED]	[REDACTED]
	[REDACTED]
[REDACTED]	[REDACTED]
[REDACTED]	

Controlled Quality Management Document		
	Sponsor:	Veru Inc.
	Protocol Number:	V3011902
STATISTICAL ANALYSIS PLAN. PHASE 2-3-4		

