#### **9.5.1.2 Change from baseline in WHO Ordinal Scale for Clinical Improvement at Day 15, Day 22 and Day 29**

Baseline for WHO Ordinal Scale for Clinical Improvement will be the last available record prior to first dose of study medication.

For subject who die, WHO Ordinal Scale for Clinical Improvement will be set to the worst possible outcome (8 – death) for the following planned timepoints to give deaths unfavorable value in the analysis. For subjects who are discharged early, or are otherwise having missing values, following timepoints use data from multiple imputation. Details for the imputation will be given in the SAP.

WHO Ordinal Scale for Clinical Improvement will be summarized using frequencies and percentages by treatment group and timepoint. Also change from baseline will be summarized.

Change from baseline will be analyzed as ordinal response using proportional odds logistic regression. Analysis will be performed separately for each timepoint (Day 15, Day 22, Day 29). Proportionality of odds will be tested and if the proportionality assumption does not hold, then non-proportional odds model will be fitted. Model will include treatment as fixed effect and study site, gender, remdesivir use (No/Yes), dexamethasone use (No/Yes) and WHO Ordinal Scale for Clinical Improvement at baseline as covariate. Odds ratio, 95% confidence interval and p-value for the treatment difference will be presented. Distribution of change from baseline will be plotted in stacked bar plot by treatment group and time point.

Proportional (or non-proportional) odds model will be performed only using the imputed data to include all subjects in the analysis.

Additionally, descriptive statistics (n, mean, standard deviation, median, minimum and maximum) will be summarized for absolute values and change from baseline by treatment group and visit.

Additionally, change from baseline will be analyzed using mixed model for repeated measures (MMRM) including treatment, visit and treatment-by-visit interaction as fixed effects and study site, gender, remdesivir use (No/Yes), dexamethasone use (No/Yes) and WHO Ordinal Scale for Clinical Improvement at baseline as covariate. The resulting F-tests will be based on Kenward-Roger's adjusted degrees of freedom. Least squares means, standard errors, 95% confidence intervals and p-values for treatments and treatment differences at each visit will be presented.

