6.11.5.2 Days in ICU

‘Days in ICU’ will be summarized using descriptive statistics (n, mean, standard deviation, median, minimum and maximum) by treatment group.

‘Days in ICU’ will be the number of days in ICU up to Day 60. In this analysis the worst possible endpoint will be assigned to those subjects who died at any time up to Day 60. For subjects who died the days in ICU will be set to 60. Even for those who were never in the ICU. If

Controlled Quality Management Document			
	Sponsor:	Veru Inc.	
	Protocol Number:	V3011902	
STATISTICAL ANALYSIS PLAN. PHASE 2-3-4			

subject did not report any days in the ICU then their days will be set to zero except for those who died.

Same analysis will be performed in subgroups for region, standard of care and WHO Ordinal Scale at baseline.

A sensitivity analysis will be performed using the actual number of days in ICU. If subject was never in the ICU then days in ICU will be set to 0 even if subject died.

Treatment comparison will be based on analysis of covariance (ANCOVA) model including treatment as a factor, and study site (or country or region), remdesivir use (No/Yes), dexamethasone use (No/Yes) and WHO Ordinal Scale strata used in randomization as covariates. Treatment difference, standard error, 95% confidence interval and p-value will be presented.

Example SAS codes for the analysis are as follows:

```
proc mixed data=XXX order=internal;
  class trt01pn site remdesivir dexamethasone;
  model response=trt01pn site remdesivir dexamethasone whostrata /
    ddfm=kr;
  lsmeans trt01pn / cl diff;
  ods output tests3=tests lsmeans=lsmeans diff=diffs
  run;
```

6.11.5.3 WHO Ordinal Scale for Clinical Improvement change from baseline to Day 15, Day 22, and Day 29

WHO Ordinal Scale for Clinical Improvement will be summarized in frequency table by visit and treatment group.

Additionally, response status for each subject will be defined based on WHO Ordinal Scale for Clinical Improvement. This analysis will compare subjects that have WHO score 0 or 1 (responder) on the visit to subjects who have WHO score ≥ 2 (non-responder) on the visit.

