Baseline for WHO Ordinal Scale is the last available record up to and including Day 1. If subject was discharged from the hospital prior to Day 15, 22 or 29 and WHO Ordinal Scale for Clinical Improvement is not collected or record is otherwise missing at those timepoints then the last available observation before or at the time of death/discharge will be carried forward. If subject dies then following time points will be set to the worst possible outcome (score=8).

Controlled Quality Management Document		
	Sponsor:	Veru Inc.
	Protocol Number:	V3011902
STATISTICAL ANALYSIS PLAN. PHASE 2-3-4		

The number and percentage of responders will be summarized by treatment group and visit.

Responders will be analyzed using similar logistic regression model except not planning multiple imputation as the above algorithm provides responder status for all subjects.

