14.2.3.6	Analysis of Covariance (ANCOVA) for Days in Intensive Care Unit (ICU) by Standard of Care - Death Assigned to Worst Possible Outcome ITT Set	Stat IP	14.2.3.2
14.2.3.7	Descriptive Statistics for Days in Intensive Care Unit (ICU) by WHO Ordinal Scale at BL - Death Assigned to Worst Possible Outcome ITT Set	IP	14.2.3.1
14.2.3.8	Analysis of Covariance (ANCOVA) for Days in Intensive Care Unit (ICU) by WHO Ordinal Scale at BL - Death Assigned to Worst Possible Outcome ITT Set	Stat IP	14.2.3.2
14.2.3.9	Descriptive Statistics for Days in Intensive Care Unit (ICU) - Actual Days ITT Set	IP	14.2.3.1
14.2.3.10	Analysis of Covariance (ANCOVA) for Days in Intensive Care Unit (ICU) - Actual Days ITT Set	Stat IP	14.2.3.2
14.2.4.1	Frequencies for WHO Ordinal Scale for Clinical Improvement by Visit ITT Set	IP	
14.2.4.2	WHO Ordinal Scale for Clinical Improvement Responders by Visit ITT Set	IP	

Controlled Quality Management Document		
	Sponsor:	Veru Inc.
	Protocol Number:	V3011902

Table Number	Table Title	Validation Method	Shell Number (if repeat)
14.2.4.3	Logistic Regression for WHO Ordinal Scale for Clinical Improvement Responders by Visit ITT Set	Stat IP	14.2.4.1
14.2.5.1	Descriptive Statistics for Days on Mechanical Ventilation - Death Assigned to Worst Possible Outcome ITT Set	IP	14.2.3.1
14.2.5.2	Analysis of Covariance (ANCOVA) for Days on Mechanical Ventilation - Death Assigned to Worst Possible Outcome ITT Set	Stat IP	14.2.3.2
14.2.5.3	Descriptive Statistics for Days on Mechanical Ventilation by Region - Death Assigned to Worst Possible Outcome ITT Set	IP	14.2.3.1
14.2.5.4	Analysis of Covariance (ANCOVA) for Days on Mechanical Ventilation by Region - Death Assigned to Worst Possible Outcome ITT Set	Stat IP	14.2.3.2
14.2.5.5	Descriptive Statistics for Days on Mechanical Ventilation by Standard of Care - Death Assigned to Worst Possible Outcome ITT Set	IP	14.2.3.1
14.2.5.6	Analysis of Covariance (ANCOVA) for Days on Mechanical Ventilation by Standard of Care - Death Assigned to Worst Possible Outcome ITT Set	Stat IP	14.2.3.2
14.2.5.7	Descriptive Statistics for Days on Mechanical Ventilation by WHO Ordinal Scale at BL - Death Assigned to Worst Possible Outcome ITT Set	IP	14.2.3.1
14.2.5.8	Analysis of Covariance (ANCOVA) for Days on Mechanical Ventilation by WHO Ordinal Scale at BL - Death Assigned to Worst Possible Outcome ITT Set	Stat IP	14.2.3.2

Controlled Quality Management Document

Sponsor: Veru Inc.

Protocol Number: V3011902

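### The SAP drops the protocol's proportional-odds analysis of the WHO score for a 0-1 versus 2-or-more split, and its list of changes misdescribes what was replaced

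*SAP*

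**What the plan says.** **Protocol 9.5.1.2.** "Change from baseline will be analyzed as ordinal response using proportional odds logistic regression". The model is fitted separately at Days 15, 22 and 29, with a non-proportional-odds model if proportionality fails, and only on multiply imputed data. A second model follows later in the section: "Additionally, change from baseline will be analyzed using mixed model for repeated measures (MMRM"), also on imputed data.

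**SAP 6.11.5.3.** The heading still names change from baseline, as does SAP 3.2. The variable tested is the score at the visit, cut in two: "This analysis will compare subjects that have WHO score 0 or 1 (responder) on the visit", against those scoring 2 or more. On the model: "Responders will be analyzed using similar logistic regression model except not planning multiple imputation". Missing scores, including those after discharge, are filled by carrying the last observation forward; deaths are set to 8.

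**SAP 11.1.** The WHO-score tables are frequencies, responder counts and "Logistic Regression for WHO Ordinal Scale for Clinical Improvement Responders by Visit". There is no ordinal model and no MMRM.

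**SAP 9.** The change is recorded in two sentences: "In the protocol WHO score was planned to be analyzed as continuous variable using MMRM", and then "However this was changed into responder type of analysis in the SAP".

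The SAP title page lists protocol version 7.0, which is the version supplied, so this is not a comparison with superseded text.

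**The concern.** There are two problems.

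First, the record of changes is inaccurate. Someone relying on SAP section 9 would think that a debatable continuous model of an ordinal score had been replaced. In fact the protocol's ordinal model was removed as well. The move from multiple imputation to carrying the last observation forward is not listed either.

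Second, the new response variable treats scores 2 to 8 as one outcome. SAP 6.2.9 gives the example of a patient discharged with a score of 2 on Day 5 who keeps that score to Day 60. If no later score is collected, that patient is a non-responder in 6.11.5.3 at every visit, as is a patient who died. When few subjects reach 0-1, a comparison at that single cut can have much less power than one that uses the whole scale.

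**Working it through.** **1. What each document plans**

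| Item | Protocol 9.5.1.2 | SAP 6.11.5.3 | Recorded in SAP 9? |
|---|---|---|---|
| Main model | Proportional odds, with fallback | Binary logistic, 0-1 vs 2+ | No, proportional odds not named |
| Additional model | MMRM | None | Yes |
| Response | Change from baseline | Visit score, dichotomised | Responder analysis named; cut-point not given |
| Missing scores | Multiple imputation | Last observation carried forward | No |
| Reason for change | n/a | n/a | None given |

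**2. The plan's own figure.** Neither document states power or an effect size for the WHO score. The sample size rests on Day 60 mortality of 5% vs 25% with 140 and 70 subjects (protocol 9.1). The interval there is −0.20 ± 1.96 × √(0.05×0.95/140 + 0.25×0.75/70) = −0.20 ± 0.1077, that is −0.308 to −0.092, which matches. I take the arm sizes and the 25% placebo deaths from there.

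**3. Assumptions.** Placebo score distributions are assumed, with 25% deaths and a 0-1 share between 5% and 60%. A common odds ratio of 2.0 turns a cumulative placebo share c into 2c/(1+c) on VERU-111. Tests are at two-sided 0.05, unadjusted and on the visit score. The ordinal test is the tie-corrected Wilcoxon test, which is the score test of the proportional-odds model. The split is tested with the pooled two-proportion test.

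**4. Power by simulation** (20,000 trials per row). Relative efficiency of the split is 3q(1−q)/(1−Σp³), where p are the pooled category shares and q is the pooled 0-1 share.

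| Placebo 0-1 share | VERU-111 0-1 share | Ordinal | Split | Relative efficiency |
|---|---|---|---|---|
| 60% | 75.0% | 63% | 61% | 0.97 |
| 45% | 62.1% | 71% | 66% | 0.91 |
| 30% | 46.2% | 75% | 63% | 0.79 |
| 15% | 26.1% | 75% | 45% | 0.55 |
| 5% | 9.5% | 77% | 18% | 0.23 |

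A second simulation on assumed distributions gave 62% vs 61%, 75% vs 63% and 75% vs 18% for shares of 60%, 30% and 5%. Across odds ratios of 1.5, 2.0 and 2.5 the split had less power in all 15 scenarios.

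**5. Check by hand, 5% row.** Assumed placebo shares for scores 0-1, 2, 3, …, 8 are 0.05, 0.20, 0.15, 0.12, 0.10, 0.08, 0.05, 0.25.
- Split: 5.0% vs 9.52%, pooled 8.02%. The null standard error is √(0.0802×0.9198×(1/140+1/70)) = 0.0397, and the alternative one is √(0.0952×0.9048/140 + 0.05×0.95/70) = 0.0360. Power = Φ((0.0452 − 1.96×0.0397)/0.0360) = Φ(−0.91) = 18%.
- Ordinal: pooled Σp³ = 0.0328. Information = 140×70×210/(3×211²) × (1−0.0328) = 14.90. Power = Φ(ln 2 × √14.90 − 1.96) = Φ(0.716) = 76%, against 77% simulated.
- Relative efficiency = 3×0.0802×0.9198/0.9672 = 0.23.

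**6. Other effect patterns**
- Mortality falls from 25% to 5% and survivors are distributed as on placebo: ordinal vs split is 83% vs 67%, 72% vs 37%, 68% vs 21%, 68% vs 10% and 67% vs 4% for 0-1 shares of 60, 45, 30, 15 and 5%.
- The whole effect moves subjects from score 2 to 0-1: the order reverses, for example 20% ordinal vs 70% split at a 30% share.

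**The case against.** **Other analyses cover the scale.** SAP 6.11.5.1 tests scores 0-4 against 5-8, and 6.11.5.6 tests death, both at Days 15, 22 and 29. Full score frequencies, mean profiles and an area under the curve are also reported. This stands. A reader might infer that the plan discards nearly all the information in the scale, or that moving from ventilation to score 2 counts as no benefit anywhere. The documents do not support that; it is true only of the responder variable in 6.11.5.3. What remains is that those are separate endpoints, the other summaries are descriptive, and no test uses the whole scale.

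**The stated reason is false.** A reader might infer that section 9 uses a wrong account of the protocol to justify the split. It does not: it gives no reason, MMRM is in the protocol, and the responder change is disclosed. The entry is incomplete and misdescribes what was replaced.

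**The power figures favour the ordinal model.** A common odds ratio is its best setting, the distributions are assumed, and the loss is about 2 points when 60% of placebo subjects score 0-1. All true. The loss is therefore conditional, although it also appears under a mortality effect of the size assumed in protocol 9.1.

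**The protocol's response variable has its own weakness.** As a change score, death from baseline 6 is +2, the same as a move from 4 to intubation at 6. The power figures are for the visit score, so they do not apply directly to restoring the protocol's model unchanged. This stands and shapes the fix.

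**The SAP may set the details.** Protocol 9.4 leaves the detailed description to the SAP. That permits a change of analysis, but not an inaccurate record of it.

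**Conclusion.** The documentary point is certain. The SAP replaces both planned models with a dichotomised responder analysis and changes the missing-data method. Section 9 names only the MMRM and gives no reason.

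The loss of power is likely but conditional. Under a common odds ratio of 2.0 it runs from about 2 points (60% of placebo subjects at 0-1) through 12 (30%) to 59 (5%). The documents give no score distribution, so the loss cannot be fixed for this trial, and it would be wrong to say that the split always loses power.

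The reach is limited. The WHO score is a secondary endpoint outside the Holm family in SAP 6.11.7 and is not the protocol's key secondary endpoint. A reader might infer a threat to the trial's main conclusion or its error rate; there is none. The change is worth making because it is cheap and because the record should be right.

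**What to change.** 1. In SAP 6.11.5.3, make a proportional-odds model at Days 15, 22 and 29 the main WHO-score analysis. Fit it preferably to the visit score with death as 8, with treatment, baseline WHO stratum and the other planned covariates, using region or country if site cannot be fitted. Keep the protocol's non-proportional fallback.
2. State one missing-data rule for this model, either the protocol's multiple imputation or a justified alternative, and say how discharged subjects are scored.
3. Keep the 0-1 versus 2+ analysis as supportive, and add the ordinal model to the table list.
4. Correct SAP section 9 to name the proportional-odds model as well as the MMRM, record any use of the visit score in place of the change score, record any change of imputation method, and give the reasons. If the sponsor prefers to keep the split as the main analysis, this step is still needed.

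The cost is one extra model per visit on data already collected, a proportionality check, and an imputation step that the SAP does not now contain for this endpoint. The primary analysis and the Holm procedure are not touched.

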11 LIST OF TABLES, FIGURES AND LISTINGS

The following table includes details of the tables, figures and listings to be included within each section of the eCTD. The following validation methods maybe used:

- Independent programming of numbers and manual review of format (IP)
- Independent programming by statistician of numbers and manual review of format (Stat IP)
- Manual review (MR)
- Code review (CR)

11.1 Tables

Table Number	Table Title	Validation Method	Shell Number (if repeat)
14.1.1.1	Subject Enrollment Enrolled Set	IP	
14.1.1.2	Screen Failures Enrolled Set	IP	
14.1.1.3	Inclusion/Exclusion Criteria Violations Enrolled Set	IP	
14.1.1.4	Analysis Sets and Subject Disposition ITT Set	IP	
14.1.1.5	Protocol Deviations ITT Set	IP	
14.1.1.6	Reasons for Exclusion from Per-Protocol Set ITT Set	IP	
14.1.1.7	Randomization by Country and Site ITT Set	IP	
14.1.2.1	Demographics ITT Set	IP	
14.1.2.2	Demographics Safety Set	IP	

Controlled Quality Management Document			
	Sponsor:	Veru Inc.	
	Protocol Number:	V3011902	
STATISTICAL ANALYSIS PLAN. PHASE 2-3-4			

Table Number	Table Title	Validation Method	Shell Number (if repeat)
14.1.2.3	Demographics mITT Set	IP	14.1.2.1
14.1.2.4	Baseline Condition ITT Set	IP	
14.1.2.5	Baseline Condition Safety Set	IP	
14.1.2.6	Baseline Condition mITT Set	IP	14.1.2.3
14.1.3.1	Previous Medical History by System Organ Class and Preferred Term ITT Set	IP	
14.1.3.2	Ongoing Medical History by System Organ Class and Preferred Term ITT Set	IP	14.1.3.1
14.1.4.1	Prior Medications by ATC Level 2 and Preferred Term ITT Set	IP	
14.1.4.2	Concomitant Medications by ATC Level 2 and Preferred Term ITT Set	IP	14.1.4.1
14.1.4.3	Background Standard of Care by Country ITT Set	IP	
14.1.5.1	Treatment Exposure Safety Set	IP	
14.1.5.2	Treatment Compliance Safety Set	IP	
14.2.1.1	Proportion of Subjects Alive by Visit ITT Set	IP	
14.2.1.2	Logistic Regression for Proportion of Subjects Alive by Visit ITT Set	Stat IP	

Controlled Quality Management Document

Sponsor: Veru Inc.

Protocol Number: V3011902

STATISTICAL ANALYSIS PLAN. PHASE 2-3-4

Table Number	Table Title	Validation Method	Shell Number (if repeat)
14.2.1.3	Proportion of Subjects Alive by Visit Safety Set	IP	14.2.1.1
14.2.1.4	Logistic Regression for Proportion of Subjects Alive by Visit Safety Set	Stat IP	14.2.1.2
14.2.1.5	Proportion of Subjects Alive by Visit mITT Set	IP	14.2.1.1
14.2.1.6	Logistic Regression for Proportion of Subjects Alive by Visit mITT Set	Stat IP	14.2.1.2
14.2.1.7	Tipping Point Analysis for Proportion of Subjects Alive at Day 60 ITT Set	Stat IP	
14.2.1.8	Logistic Regression for Proportion of Subjects Alive by Visit - Identity Link ITT Set	Stat IP	14.2.1.2
14.2.1.9	Kaplan-Meier Estimates for Overall Mortality ITT Set	Stat IP	
14.2.1.10	Cox Proportional Hazards Model for Overall Mortality ITT Set	Stat IP	
14.2.1.11	Proportion of Subjects Alive by Region, Country and Site, and Visit ITT Set	IP	14.2.1.1
14.2.1.12	Logistic Regression for Proportion of Subjects Alive by Region and Visit ITT Set	Stat IP	14.2.1.2
14.2.1.13	Proportion of Subjects Alive by Standard of Care and Visit ITT Set	IP	14.2.1.1
14.2.1.14	Logistic Regression for Proportion of Subjects Alive by Standard of Care and Visit ITT Set	Stat IP	14.2.1.2

	
	
	
	

Controlled Quality Management Document		
	Sponsor:	Veru Inc.
	Protocol Number:	V3011902

Table Number	Table Title	Validation Method	Shell Number (if repeat)
14.2.1.15	Proportion of Subjects Alive by WHO Ordinal Scale at BL and Visit ITT Set	IP	14.2.1.1
14.2.1.16	Logistic Regression for Proportion of Subjects Alive by WHO Ordinal Scale at BL and Visit ITT Set	Stat IP	14.2.1.2
14.2.1.17	Proportion of Subjects Alive by Vaccination Status (All Vaccinated (at Least One Shot) vs. All Unvaccinated) and Visit ITT Set	IP	14.2.1.1
14.2.1.18	Proportion of Subjects Alive by Vaccination Status (All Vaccinated with US Acceptable Vaccine vs. the Rest of the Population) and Visit ITT Set	IP	14.2.1.1
14.2.1.19	Proportion of Subjects Alive by Vaccination Status (All Vaccinated with at Least One Shot within 6 Months of the First Dose on V3011902 vs. the Rest of the Population) and Visit ITT Set	IP	14.2.1.1
14.2.2.1	Proportion of Subjects Alive and Free of Respiratory Failure by Visit ITT Set	IP	14.2.1.1
14.2.2.2	Logistic Regression for Proportion of Subjects Alive and Free of Respiratory Failure by Visit ITT Set	Stat IP	14.2.1.2
14.2.3.1	Descriptive Statistics for Days in Intensive Care Unit (ICU) - Death Assigned to Worst Possible Outcome ITT Set	IP	
14.2.3.2	Analysis of Covariance (ANCOVA) for Days in Intensive Care Unit (ICU) - Death Assigned to Worst Possible Outcome ITT Set	Stat IP	

Controlled Quality Management Document		
	Sponsor:	Veru Inc.
	Protocol Number:	V3011902

Table Number	Table Title	Validation Method	Shell Number (if repeat)
14.2.3.3	Descriptive Statistics for Days in Intensive Care Unit (ICU) by Region - Death Assigned to Worst Possible Outcome ITT Set	IP	14.2.3.1
14.2.3.4	Analysis of Covariance (ANCOVA) for Days in Intensive Care Unit (ICU) by Region - Death Assigned to Worst Possible Outcome ITT Set	Stat IP	14.2.3.2
14.2.3.5	Descriptive Statistics for Days in Intensive Care Unit (ICU) by Standard of Care - Death Assigned to Worst Possible Outcome ITT Set	IP	14.2.3.1
14.2.3.6	Analysis of Covariance (ANCOVA) for Days in Intensive Care Unit (ICU) by Standard of Care - Death Assigned to Worst Possible Outcome ITT Set	Stat IP	14.2.3.2
14.2.3.7	Descriptive Statistics for Days in Intensive Care Unit (ICU) by WHO Ordinal Scale at BL - Death Assigned to Worst Possible Outcome ITT Set	IP	14.2.3.1
14.2.3.8	Analysis of Covariance (ANCOVA) for Days in Intensive Care Unit (ICU) by WHO Ordinal Scale at BL - Death Assigned to Worst Possible Outcome ITT Set	Stat IP	14.2.3.2
14.2.3.9	Descriptive Statistics for Days in Intensive Care Unit (ICU) - Actual Days ITT Set	IP	14.2.3.1
14.2.3.10	Analysis of Covariance (ANCOVA) for Days in Intensive Care Unit (ICU) - Actual Days ITT Set	Stat IP	14.2.3.2
14.2.4.1	Frequencies for WHO Ordinal Scale for Clinical Improvement by Visit ITT Set	IP	
14.2.4.2	WHO Ordinal Scale for Clinical Improvement Responders by Visit ITT Set	IP	

Controlled Quality Management Document		
	Sponsor:	Veru Inc.
	Protocol Number:	V3011902

Table Number	Table Title	Validation Method	Shell Number (if repeat)
14.2.4.3	Logistic Regression for WHO Ordinal Scale for Clinical Improvement Responders by Visit ITT Set	Stat IP	14.2.4.1
14.2.5.1	Descriptive Statistics for Days on Mechanical Ventilation - Death Assigned to Worst Possible Outcome ITT Set	IP	14.2.3.1
14.2.5.2	Analysis of Covariance (ANCOVA) for Days on Mechanical Ventilation - Death Assigned to Worst Possible Outcome ITT Set	Stat IP	14.2.3.2
14.2.5.3	Descriptive Statistics for Days on Mechanical Ventilation by Region - Death Assigned to Worst Possible Outcome ITT Set	IP	14.2.3.1
14.2.5.4	Analysis of Covariance (ANCOVA) for Days on Mechanical Ventilation by Region - Death Assigned to Worst Possible Outcome ITT Set	Stat IP	14.2.3.2
14.2.5.5	Descriptive Statistics for Days on Mechanical Ventilation by Standard of Care - Death Assigned to Worst Possible Outcome ITT Set	IP	14.2.3.1
14.2.5.6	Analysis of Covariance (ANCOVA) for Days on Mechanical Ventilation by Standard of Care - Death Assigned to Worst Possible Outcome ITT Set	Stat IP	14.2.3.2
14.2.5.7	Descriptive Statistics for Days on Mechanical Ventilation by WHO Ordinal Scale at BL - Death Assigned to Worst Possible Outcome ITT Set	IP	14.2.3.1
14.2.5.8	Analysis of Covariance (ANCOVA) for Days on Mechanical Ventilation by WHO Ordinal Scale at BL - Death Assigned to Worst Possible Outcome ITT Set	Stat IP	14.2.3.2

Controlled Quality Management Document

Sponsor: Veru Inc.

Protocol Number: V3011902

STATISTICAL ANALYSIS PLAN. PHASE 2-3-4

Table Number	Table Title	Validation Method	Shell Number (if repeat)
14.2.5.9	Descriptive Statistics for Days on Mechanical Ventilation - Actual Days ITT Set	IP	14.2.3.1
14.2.5.10	Analysis of Covariance (ANCOVA) for Days on Mechanical Ventilation - Actual Days ITT Set	Stat IP	14.2.3.2
14.2.6.1	Descriptive Statistics for Days in Hospital - Death Assigned to Worst Possible Outcome ITT Set	IP	14.2.3.1
14.2.6.2	Analysis of Covariance (ANCOVA) for Days in Hospital - Death Assigned to Worst Possible Outcome ITT Set	Stat IP	14.2.3.2
14.2.6.3	Descriptive Statistics for Days in Hospital by Region - Death Assigned to Worst Possible Outcome ITT Set	IP	14.2.3.1
14.2.6.4	Analysis of Covariance (ANCOVA) for Days in Hospital by Region - Death Assigned to Worst Possible Outcome ITT Set	Stat IP	14.2.3.2
14.2.6.5	Descriptive Statistics for Days in Hospital by Standard of Care - Death Assigned to Worst Possible Outcome ITT Set	IP	14.2.3.1
14.2.6.6	Analysis of Covariance (ANCOVA) for Days in Hospital by Standard of Care - Death Assigned to Worst Possible Outcome ITT Set	Stat IP	14.2.3.2
14.2.6.7	Descriptive Statistics for Days in Hospital by WHO Ordinal Scale at BL - Death Assigned to Worst Possible Outcome ITT Set	IP	14.2.3.1
14.2.6.8	Analysis of Covariance (ANCOVA) for Days in Hospital by WHO Ordinal Scale at BL - Death Assigned to Worst Possible Outcome ITT Set	Stat IP	14.2.3.2

Controlled Quality Management Document		
	Sponsor:	Veru Inc.
	Protocol Number:	V3011902

Table Number	Table Title	Validation Method	Shell Number (if repeat)
14.2.6.9	Descriptive Statistics for Days in Hospital - Actual Days ITT Set	IP	14.2.3.1
14.2.6.10	Analysis of Covariance (ANCOVA) for Days in Hospital - Actual Days ITT Set	Stat IP	14.2.3.2
14.2.7.1	Viral Load Descriptive Statistics ITT Set	IP	
14.2.7.2	Analysis of Covariance (ANCOVA) for Change from Baseline in Viral Load ITT Set	Stat IP	14.2.3.2
14.2.8.1	Area Under Curve of WHO Ordinal Scale for Clinical Improvement ITT Set	IP	
14.2.9.1	Summary of Primary and Key Secondary Efficacy Endpoints (Holm Step-down Procedure) ITT Set	Stat IP	
14.3.1.1.1	Overall Summary of Adverse Events Safety Set	IP	
14.3.1.2.1	TEAEs by System Organ Class and Preferred Term Safety Set	IP	
14.3.1.2.2	Treatment-Related TEAEs by System Organ Class and Preferred Term Safety Set	IP	14.3.1.2.1
14.3.1.2.3	Serious TEAEs by System Organ Class and Preferred Term Safety Set	IP	14.3.1.2.1
14.3.1.2.4	Treatment-Related Serious TEAEs by System Organ Class and Preferred Term Safety Set	IP	14.3.1.2.1

Controlled Quality Management Document			
	Sponsor:	Veru Inc.	
	Protocol Number:	V3011902	
STATISTICAL ANALYSIS PLAN. PHASE 2-3-4			

Table Number	Table Title	Validation Method	Shell Number (if repeat)
14.3.1.2.5	TEAEs Leading to Treatment Modification (drug interrupted / dose increased / dose reduced) by System Organ Class and Preferred Term Safety Set	IP	14.3.1.2.1
14.3.1.2.6	TEAEs Leading to Treatment Discontinuation (drug withdrawn) by System Organ Class and Preferred Term Safety Set	IP	14.3.1.2.1
14.3.1.2.7	Fatal TEAEs by System Organ Class and Preferred Term Safety Set	IP	14.3.1.2.1
14.3.1.3.1	TEAEs by System Organ Class, Preferred Term and Maximum Toxicity Grade Safety Set	IP	
14.3.1.3.2	TEAEs by System Organ Class, Preferred Term and Strongest Relationship to Study Treatment Safety Set	IP	
14.3.2.1	Listing of Deaths Safety Set	IP	
14.3.2.2	Listing of Serious TEAEs Safety Set	IP	14.3.2.1
14.3.4.1	Listing of Abnormal Laboratory Values Safety Set	IP	
14.3.5.1.1	Hematology Descriptive Statistics Safety Set	IP	14.2.7.1
14.3.5.1.2	Hematology Shift Table Safety Set	IP	
14.3.5.2.1	Chemistry Descriptive Statistics Safety Set	IP	14.2.7.1
14.3.5.2.2	Chemistry Shift Table Safety Set	IP	14.3.5.1.2

Controlled Quality Management Document		
	Sponsor:	Veru Inc.
	Protocol Number:	V3011902

Table Number	Table Title	Validation Method	Shell Number (if repeat)
14.3.5.3.1	Urinalysis Descriptive Statistics (Continuous) Safety Set	IP	14.2.7.1
14.3.5.3.2	Urinalysis Descriptive Statistics (Categorical) Safety Set	IP	14.2.1.1
14.3.5.3.3	Urinalysis Shift Table Safety Set	IP	14.3.5.1.2
14.3.6.1.1	Vital Signs Descriptive Statistics Safety Set	IP	14.2.7.1
14.3.7.1.1	Physical Examination Shift Table Safety Set	IP	14.3.5.1.2
14.3.8.1.1	ECG Descriptive Statistics Safety Set	IP	14.2.7.1
14.3.8.1.2	ECG Shift Table Safety Set	IP	14.3.5.1.2
14.3.9.1.1	Chest X-Ray / CT Shift Table Safety Set	IP	14.3.5.1.2
14.4.1.1	Descriptive Statistics for Pharmacokinetic Concentrations of Veru-111 (ng/mL) Safety Set	IP	

Controlled Quality Management Document		
	Sponsor:	Veru Inc.
	Protocol Number:	V3011902

